APPENDIX B: QT-PROLONGING DRUGS WITH A KNOWN RISK FOR TORSADE DE POINTES

It is the responsibility of each Investigator to check this list periodically for new additions.

Please refer to the following website for the most recent information:

https://crediblemeds.org/pdftemp/pdf/CombinedList.pdf

Antiarrhythmics

- Amiodarone (Cordarone, Pacerone)
- Bepridil (Vascor)
- Disopyramide (Norpace)
- Dofetilide (Tikosyn)
- Dronedarone (Multaq)
- Flecainide (Tambocor)
- Hydroquinidine (Serecor)
- Ibutilide (Corvert)
- Nifekalant (Shinbit)
- Procainamide (Pronestyl, Procan)
- Quinidine (Cardioquin, Quinaglute)
- Sotalol (Betapace)

Antibiotics

- Azithromycin (Zithromax)
- Ciprofloxacin (Cipro, Otiprio, Ciloxan)
- Clarithromycin (Biaxin)
- Erythromycin (Erythrocin, EES)
- Gatifloxacin (Tequin)
- Grepafloxacin (Raxar)
- Levofloxacin (Levaquin, Tavanic)
- Moxifloxacin (Avelox)
- Pentamidine (NebuPent, Pentam)
- Roxithromycin (Rulide)
- Sparfloxacin (Zagam)

Antidepressant

- Citalopram (Celexa)
- Escitalopram (Cipralex)

Anti-emetics

- Chlorpromazine (Thorazine, Largactil, Megaphen)
- Domperidone (Motilium)
- Droperidol (Inapsine)
- Ondansetron (Zofran)

Anticancer

- Aclarubicin (Aclacin)
- Oxiplatin (Eloxatin)
- Vandetanib (Caprelsa)

Antifungal

- Fluconazole (Diflucan, Trican)
- Pentamidine (Pentam)

Antihistamine

- Astemizole (Hismanal)
- Terfenadine (Seldane)

Anticholesterolemic

• Probucol (Lorelco)

Antimalarials

- Chloroquine (Aralen)
- Halofantrine (Halfan)
- Hydroxychloroquine (Plaquenil)

Antipsychotics

- Chlorpromazine (Thorazine)
- Chlorprothixene (Truxal)
- Haloperidol (Haldol)
- Levomepromazine (Nosinan, Levoprome)
- Levosulpiride (Lesuride, Eliva)
- Mesoridazine (Serentil)
- Pimozide (Orap)
- Sulpiride (Dogmatil)
- Sultopride (Barnetil, Barnotil, Topral)
- Thioridazine (Mellaril)

Gastrointestinal Stimulant

• Cisapride (Propulsid)

Opiate Agonists

- Levomethadyl acetate (Orlaam)
- Methadone (Dolophine, Methadose)

Confidential and Proprietary

Rain Therapeutics Inc.

Other

- Anagrelide (Agrylin)
- Arsenic trioxide (Trisenox)
- Cesium chloride
- Cocaine
- Cilostazol (Pletal)
- Donepezil (Aricept)
- Ibogaine
- Papaverine hydrochloride (intracoronary)
- Propofol (Diprivan)Sevoflurane (Ultane)
- Terlipressin (Teripress, Glypressin)
- Terodiline (Micturin)

Confidential and Proprietary

DECLARATION OF THE INVESTIGATOR

Table 7 Clinical Laboratory Parameters	45 46
Table 7 Clinical Laboratory Parameters  Table 8 Site 101 Units and Reference Ranges by Parameter  Table 9 Site 102 Units and Reference Ranges by Parameter  Table 10 Site 103 Units and Reference Ranges by Parameter  Table 11 Site 104 Units and Reference Ranges by Parameter  Table 12 Site 105 Units and Reference Ranges by Parameter	45 46
Table 7 Clinical Laboratory Parameters	45 46 47

## 

List of Abbreviations	and Definition	of Terms
-----------------------	----------------	----------

	List of Abbreviations and Definition of Terms
Abbreviation	Description
ADaM	analysis data model
AE	adverse event
ALT	alanine aminotransferase
AST	aspartate aminotransferase
ATC	Anatomical / Therapeutic / Chemical
BOR	best overall response
CI	confidence interval
CDISC	Clinical Data Interchange Standards Consortium
CM	concomitant medication
CR	complete response
CSR	clinical study report
CT	computed tomography
ctDNA	circulating tumor deoxyribonucleic acids
CTCAE	Common Terminology Criteria for Adverse Events
DCR	disease control rate
DOR	duration of response
ECG	electrocardiogram
ECOG	Eastern Cooperative Oncology Group
eCRF	electronic case report form
EGFR	epidermal growth factor receptor
EOI	End of infusion
EOT	End-of-Treatment Visit
ERBB2	v-erb-b2 avian erythroblastic leukemia viral oncogene homolog 2
ERBB4	erb-b2 Receptor tyrosine kinase 4
FDA	Food and Drug Administration
HER	human epidermal growth factor receptor
HR	heart rate
ICH	International Council for Harmonisation
IV	intravenous
MedDRA	Medical Dictionary for Regulatory Activities
MRI	magnetic resonance imaging
NCI	National Cancer Institute
NRG1	neuregulin 1
NSCLC	non-small cell lung cancer
ORR	objective response rate

## Rain Therapeutics Inc.

RAIN-701 SAP

Version 1.0, 14 October 2022

Abbreviation	Description
OS	overall survival
PAS	Primary analysis set
PD	progressive disease
PET	positron emissions tomography
PFS	progression-free survival
PK	pharmacokinetic
PO	oral
PR	partial response
QTc	corrected QT interval
QTcF	corrected QTc interval as calculated according to Fridericia's formula
RECIST	Response Evaluation Criteria in Solid Tumors
SAE	serious adverse event
SAP	statistical analysis plan
SD	stable disease (tumor response)
SD	standard deviation (statistics)
SOC	system organ class
STEAP4	six transmembrane epithelial antigen of the prostate, family member 4
TEAE	treatment-emergent adverse event
TLF	tables, listings, and figures
WHO	World Health Organization
WOCBP	women of childbearing potential

Version 1.0, 14 October 2022

#### 1 REVISION HISTORY

Version	Date	Document Owner	Revision Summary
1.0	14 October 2022	[name]	Initial version

#### 2 RELATED DOCUMENTS: PROTOCOL AND CASE REPORT FORMS

Version	Date
Initial Protocol	14Dec2018
Protocol (Amendment 1)	06Mar2019
Protocol (Amendment 2)	17Jun2019
Protocol (Amendment 2.1)	11Nov2019
Protocol (Amendment 3)	24Oct2020
Case Report Forms	22Mar2019

#### 3 COMMITMENT TO GOOD STATISTICAL PRACTICE

## 3.1 Definition of Good Statistical Practice

The International Council for Harmonisation Guideline on Statistical Principles for Clinical Trials (ICH E9) implicitly defines good statistical practice. Good statistical practice includes both appropriate statistical designs to minimize bias and maximize precision of analysis plus operational excellence to assure credibility of results. The scientific design associated with any clinical trial is found in the protocol and a more detailed, pre-specified statistical analysis plan such as this one presents the final statistical methods.

We interpret the operational side of good statistical practice as a transparent, reproducible, and validated approach to acquiring and analyzing clinical trial data. Reproducible research depends upon process transparency and also provides auditability of the statistical analysis. Analysis transparency requires that a navigable electronic process chain exists from defining the objective of the analysis to creating the results.

#### 3.2 Use of Standards

Data standards are foundational for creating an environment where tools can be leveraged at different points in the analysis process. Data standards for clinical development of drugs have been defined and are maturing under various initiatives through the Clinical Data Interchange

Version 1.0, 14 October 2022

Standards Consortium (CDISC). RAIN Therapeutics uses raw, source data sets and Analysis Data Model (ADaM) statistical analysis files for producing analysis results. Other applicable standards include regulatory guidance from the Food and Drug Administration (FDA) and ICH:

- ICH Guideline on the Structure and Content of Clinical Study Reports (ICH E3)
- ICH Guideline for Good Clinical Practice (ICH E6)

#### 4 PURPOSE OF THE ANALYSIS PLAN

This statistical analysis plan (SAP) pre-specifies the statistical analysis methods for supporting the completion of the abbreviated clinical study report (CSR) of Study RAIN-701 for investigational product tarloxotinib, a novel drug candidate designed to treat subjects with advanced solid tumors with qualifying genetic mutations and/or fusions. The study intended to enroll up to 215 subjects across 5 cohorts but was discontinued early on the basis of a business decision made by the sponsor. At the time of the database lock for RAIN-701 (23 April 2021), 41 subjects were enrolled. This SAP will be used to conduct a comprehensive safety analysis and summarize the available efficacy data collected during the study. The primary, secondary, and efficacy analyses planned in the protocol may not be appropriate or possible based on the available data. The planned analyses identified in this SAP may be included in future manuscripts.

The analysis methods described in this plan are considered *a posterior*, in that they have been defined after the clinical database lock. Exploratory analyses that are not defined in this SAP may be performed to support the clinical development program. Any post-hoc or unplanned analyses that are performed for the CSR, but not defined in this SAP, will be documented in the CSR. Changes from the planned analyses stated in the study protocol are described in Section 15. Should the SAP and the protocol be inconsistent with respect to any further planned analyses, the language of the SAP is governing.

Version 1.0, 14 October 2022

#### 5 STUDY OBJECTIVE

This study was planned to evaluate the safety and efficacy of tarloxotinib 150 mg/m² as a weekly 1-hour intravenous (IV) infusion of up to 40 weeks when administered to subjects with non-small cell lung cancer (NSCLC) whose tumors harbor either an epidermal growth factor receptor (EGFR) exon 20 insertion or a human epidermal growth factor receptor 2 (HER2)-activating mutation (including exon insertions).

## 5.1 Efficacy Objectives and Endpoints

The primary, secondary, and efficacy analyses planned in the protocol may not be appropriate or possible based on the available data. Additionally, efficacy analyses are unlikely to be significant because the sample size is small and the analyses will be underpowered. In place of formal efficacy analyses, selected efficacy endpoints will be summarized descriptively.

## 5.1.1 Primary Efficacy

The analysis of the primary objective as outlined in the study protocol will not be performed for the abbreviated CSR, but will instead be summarized descriptively and listed where possible. The primary objective of this study was the evaluation of the objective response rate (ORR), based on subjects who had complete response or partial response, of tarloxotinib according to Response Evaluation Criteria in Solid Tumors (RECIST) version 1.1.

## 5.1.2 Secondary Efficacy

The analyses of the secondary objectives as outlined in the study protocol will not be performed for the abbreviated CSR, but will instead be summarized descriptively and listed where possible. Secondary objectives include evaluation of the antitumor effect of tarloxotinib on: best overall response (BOR), duration of response (DOR), disease control rate (DCR), progression-free survival (PFS), and overall survival (OS) as measured from the date of first study drug dose to the date of death by any cause. Additional secondary efficacy endpoints such as the exploration of pharmacokinetics of tarloxotinib and tarloxotinib-E; and the determination of whether there is

an association between plasma exposure to tarloxotinib and effects on cardiac repolarization will not be performed because of the limited data basis.

## 5.1.3 Exploratory Efficacy

The analyses of the exploratory objectives as outlined in the study protocol will not be performed for the abbreviated CSR because of the limited data basis. Exploratory objectives are described in Protocol Section 4.2.3.

## 5.2 Safety Objective

The safety objective of the study is to evaluate the safety of tarloxotinib subjects with NSCLC using safety assessments described in Section 6.3.2. Safety endpoints include the incidence of treatment-emergent adverse events (TEAEs); changes in clinical laboratory parameters (hematology, serum chemistry, and urinalysis), vital signs, and electrocardiogram (ECG) parameters; physical examination results; and use of concomitant medications (CMs).

#### 6 STUDY DESIGN

#### 6.1 Overall Study Design

This was a Phase 2 multicenter, open-label study to evaluate the antitumor effect of tarloxotinib in subjects with NSCLC whose tumors harbors either an EGFR exon 20 insertion or a HER2-activating mutation (including exon 20 insertions) or subjects with advanced solid tumors expressing NRG1/HER-family gene fusions or a HER2-activating. All subjects have received at least 1 prior platinum-based chemotherapy-containing regimen in the advanced/metastatic setting (Cohorts A, B, and B1) or standard of care for cancer (Cohorts C and D). Cohorts B1 and D were not be pursued at the discretion of the Sponsor.

Table 1 RAIN-701 Number of Subjects by Cohort

Cohort	Description	Planned N	Enrolled N
A:	Subjects with advanced NSCLC harboring an EGFR exon 20 insertion mutation o At least 1 prior platinum-based chemotherapy-containing regimen	43	11
B:	Subjects with advanced NSCLC with a HER2 activating mutation	43	22

Version 1.0, 14 October 2022

	Subjects who have received at least 1 prior platinum-based chemotherapy-containing regimen		
B1*	
 
Subjects with advanced NSCLC harboring a HER2-activating mutation
 
Subjects who have received at least 1 platinum-based chemotherapy-containing regimen
 
Subjects who have received prior HER2-directed therapy
 
	43	0
C:	
 
Subjects with advanced solid tumors who have failed standard therapies appropriate for their tumor type and stage of disease, or, in the opinion of the Investigator, would be unlikely to tolerate or derive clinically meaningful benefit from appropriate standard-of-care therapy
 
Subjects with tumors harboring an NRG1 gene fusion, EGFR gene fusion, EGFR kinase domain duplication, ERBB2 gene fusion, or ERBB4 gene fusion
 
	43	8
D*:	
 
Subjects with advanced solid tumors who have failed all standard therapies appropriate for their tumor type and stage of disease, or, in the opinion of the Investigator, would be unlikely to tolerate or derive clinically meaningful benefit from appropriate standard-of-care therapy
 
Subjects with tumors (excluding NSCLC) harboring a HER2-activating mutation
 
	43	0
Total		215	41

[figure not shown]
Approximately 248 subjects were planned for enrollment on the study to yield 215 evaluable subjects, 43 subjects per cohort. A total of 41 subjects were enrolled in cohorts A, B and C. No subjects were enrolled on cohorts C and D. All cohorts used a Simon's 2-stage design. In the first stage, 21 subjects were accrued. If more than 3 subjects in a cohort had a partial or complete response, up to 22 additional subjects could have been enrolled to the cohort, for up to a total of 43 subjects per cohort. However, if there were 3 or fewer responses among these 21 subjects, the cohort would be stopped based on futility.

Subjects received taroxontinib 150 mg/m^2 administered as a weekly 1-hour IV infusion on Days 1, 8, 15, and 22 of each 28-day cycle until disease progression or unacceptable toxicity (e.g., hepatotoxicity meeting Hy's law criteria or serious arrhythmias of ventricular origin).

\* Cohorts B1 and/or D were not pursued, at the discretion of the Sponsor

Subjects were expected to receive up to 10 cycles of treatment. The total study duration was estimated to be 36 months, including approximately 24 months for accrual and approximately 12 months for follow-up after the last subject was enrolled. Upon completion of the end of treatment visit, subjects returned to the clinic within 30 days following their last dose for a Follow-up visit. Clinical visits during the Treatment Period and Follow-up Period included efficacy, biomarkers, safety, and pharmacokinetic (PK) assessments. Figure 1 depicts study visits from Screening Period to Follow-up Period. The maximum duration of Study RAIN-701 per subject was expected to be up to 338 days (i.e., a maximum of 28-day Screening Period, a Treatment Period consisting of a maximum of ten 28-day treatment cycles, and a 30-day safety Follow-up Period). Assessments and procedures for evaluation of safety, efficacy, PK, and biomarkers were conducted per the protocol-specified schedule (see Table 2).

Figure 1 Schema of Study RAIN-701

Days 1, 8, 15, and 22 of every 28-day cycle

#### **6.2** Study Medication

#### 6.2.1 Tarloxotinib

Tarloxotinib 150 mg/m² was administered as a 1-hour IV infusion weekly until progressive disease (PD) or unacceptable toxicity. Tarloxotinib was administered on Day 1, Day 8, Day 15, and Day 22 of every 28-day cycle. All infusions after Cycle 1 Day 1 were administered 7 days  $\pm$  1 day after the prior infusion.

## **6.2.2** Potassium Supplementation

Serum electrolytes (including potassium) were checked prior to each tarloxotinib infusion. Subjects with a pre-infusion serum potassium of < 3.5 mEq/L received potassium replacement

<sup>2 Every 8 weeks( $\pm$  5 days) from Cycle 1 Day 1

per institutional policy (IV and/or oral [PO]) and have the scheduled tarloxotinib infusion delayed at least 24 hours and potassium levels rechecked within 1 hour prior to the rescheduled infusion. All subjects with a pre-infusion serum potassium levels  $\geq 3.5$  mEq/L and  $\leq 5.0$  mEq/L were supplemented daily with 40 mEq/L of potassium replacement per institutional policy (IV and/or PO).

#### 6.2.3 Premedication

All subjects may have received steroid or anti-emetics premedication prior to tarloxotinib infusions. The premedication regimen was determined by the Investigator and may be adjusted at subsequent infusions based on the signs and symptoms observed during or after prior infusions.

#### 6.3 Assessments

Table 2 shows the schedule of events for the study.

## **6.3.1** Efficacy Assessments

Tumor assessment and imaging was performed according to institutional practice and included computerized tomography (CT) or magnetic resonance imaging (MRI) of the chest and abdomen, brain scan, and bone scan at baseline. The baseline radiographic tumor assessment was required within 28 days prior to the first dose of tarloxotinib, at the Screening assessment. Brain and bone scans did not need to be repeated for subjects with no brain or bone metastases at baseline. Recently completed negative positron emissions tomography (PET) scans could be substituted for baseline bone scans. Subsequent radiographic tumor assessments were every 8 weeks (± 5 days) with respect to Cycle 1 Day 1 (e.g., Cycle 3 Day 1, Cycle 5 Day 1, etc.), until unequivocal PD was documented. The same imaging modality used for baseline imaging (i.e., CT or MRI) was used for subsequent tumor assessments in each subject. In accordance with RECIST v1.1, response (partial response [PR] and complete response [CR]) was confirmed by a second tumor assessment at least 4 weeks after the initial observed response. The scheduling of subsequent tumor assessments may have been adjusted based on the date of the most recent imaging.

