	Appendix B: Update the list of medications with a known risk for TdP	
	Include additional minor changes for clarity and consistency	

Confidential and Proprietary

Amendment 2.1	Amendment 2	The protocol was amended to:		
11 November 2019	17 June 2019	• Section 4: Modify total number of patients to 83 (20 patients in Cohorts A and B and 43 patients in Cohort C) and add that Cohort C will use a Simon 2-stage design		
		 Section 4.2.1 Increase confirmation of primary endpoint from 4 weeks to 8 weeks after initial documentation 		
		Section 5.1: Add details of prior therapy for Cohort C		
		Section 5.2: Add exclusion criteria for upper limit of ALT, AST, and bilirubin values		
		Section 6.7: Clarify treatment guidelines for QTc prolongation		
		Section 8.5: Clarify reporting procedures for QTc prolongation		
		Section 9.1: Add determination of Cohort C sample size		
		Include additional minor changes for clarity and consistency		
Amendment 2	Amendment 1	The protocol was amended to:		
17 June 2019	01 March 2019	Revise the protocol title to reflect the addition of Cohort C		
		 Add new Section 2.2.2: Add study population background and rationale for the inclusion of patients with solid tumors and NRG1/HER-family gene fusions (Cohort C) 		
		Section 4 (and throughout): Include a 3 rd cohort (Cohort C) of patients with advanced solid tumors that harbor NRG1 or HER-family gene fusions		
		• Section 4: Modify total number of patients to 60 (20 patients each in Cohorts A, B, and C) and add that Cohort C will use a Simon's 2-stage design		
		Section 5: Expand Table 3 to include NRG1 and HER-family gene fusions		
		Section 5.1: Add details of prior therapy for Cohort C		
		Section 6.4: Revise potassium supplementation guidelines.		
		• Section 6.7: Provide further description of the QTc prolongation observed in prior tarloxotinib studies and clarify treatment guidelines for QTc prolongation		
		• Section 6.9.2: Clarify that a window of ± 10 minutes is acceptable for all timed assessments relative to infusions		

Rain	Thera	peutics	Inc
1 Culli	1 IICI U	peanes	m.

Confidential and Proprietary

		• Section 6.9.2: Clarify that the optional tumor biopsy may be performed after any study treatment infusion in consenting patients
		• Created new Section 8.1.1.5: Move the information on SUSAR reporting timeframe out of Section 8.3 (SAEs)
		Section 8.5: Clarify reporting procedures for QTc prolongation
		Section 9.1: Add determination of Cohort C sample size

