4.2 Endpoints and Criteria for Evaluation

4.2.1 Primary Endpoint

The primary efficacy endpoint is ORR based on patients who had PR or complete response (CR) with confirmation at least 8 weeks after initial documentation. Tumor response will be assessed by the investigators in accordance with RECIST v1.1. If disease progression according to RECIST v1.1 is documented at any time, no further disease response assessment will be required. Patients who are alive with no objective documentation of disease progression by the data cut-off date for ORR analysis will be censored at the date of their last evaluable tumor assessment.

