7. ASSESSMENT OF EFFICACY

Tumor assessment and imaging will be performed according to institutional practice and will include CT or MRI of the chest and abdomen, brain scan, and bone scan at baseline. The baseline radiographic tumor assessment is required within 28 days prior to the first dose of tarloxotinib. Brain and bone scans do not need to be repeated for patients with no brain or bone metastases at baseline. Recently completed negative positron emissions tomography (PET) scans can be substituted for baseline bone scans. Subsequent radiographic tumor assessments will be every 8 weeks (±5 days) with respect to Cycle 1 Day 1, until unequivocal PD is documented. The same imaging modality used for baseline imaging (i.e., CT or MRI) must be used for subsequent tumor assessments in each patient. In accordance with RECIST v1.1, response (PR and CR) must be confirmed by a second tumor assessment at least 8 weeks after the initial observed response. The scheduling of subsequent tumor assessments may be adjusted based on the date of the most recent imaging. Investigators are instructed to ensure that original

Confidential and Proprietary

images (or high-quality copies) of all baseline and on-study scans are filed and available for transmission to the Sponsor (or designee) for a future possible central reading.

Efficacy assessment will be according to the local Investigator.

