#### 15 CHANGES RELATIVE TO THE PROTOCOL-SPECIFIED ANALYSIS

Protocol Section 9.2.3 states "Deviations will be defined prior to database lock. Handling of major deviations in statistical analyses will be defined in the SAP" and further defines a Per-Protocol analysis set excludes subjects with certain, pre-specified deviations. RAIN-701 was terminated and the analysis will support an abbreviated clinical study report, which does not include protocol deviations per FDA guidance for industry, Submission of Abbreviated Reports and Synopses in Support of Marketing Applications. Analysis will be performed on the safety population which includes all subjects who received at least 1 dose of tarloxotinib. Analysis of a Per Protocol (PP) population where subjects with major protocol deviations are removed is not necessary for the aCSR. The abbreviated CSR will provide a comprehensive safety analysis for all subjects receiving at least 1 dose of tarloxotinib. Additionally, the primary efficacy analysis of ORR will include all treated subjects. Efficacy analyses are not interpretable as RAIN-701 was terminated and did not enroll the intended sample size to support statistical analyses.

Protocol Section 7 states, "In accordance with RECIST v1.1, response (PR and CR) must be confirmed by a second tumor assessment at least 8 weeks after the initial observed response." SAP Section 6.3.1 text instead states that the confirmation assessment must be at least 4 weeks after the initial observed response, which is aligned with the true RECIST v1.1 criteria. The efficacy endpoint (Section 9.2.13) still follows the protocol text in defining the disease control for at least 8 weeks (2 cycles).

Protocol Table 12 states "Microscopic sediment evaluation, as clinically indicated" as a urinalysis assessment, but these microscopic sediment urinalysis assessments were not collected. Similarly, Protocol Table 12 lists ALP as a serum chemistry assessment, but it was not collected.

Units and reference ranges of the local laboratory assessments were not collected. The Sponsor has assigned units and lab normal ranges for each parameter (e.g., lower limit of normal, upper limit of normal) based on available information and Harrison's Principles of Internal Medicine (Appendix A).

Rain Therapeutics Inc. RAIN-701 SAP

Version 1.0, 14 October 2022

Adverse events were coded with MedDRA version 22.0 and medical history events were coded with MedDRA version 23.0.

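### The SAP, defined after database lock, shortens response confirmation from 8 to 4 weeks and plans no ORR under the protocol's rule

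*SAP*

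**What the plan says.** **Protocol.** Section 4.2.1 defines the primary endpoint as ORR based on PR or CR "with confirmation at least 8 weeks after initial documentation". Section 7 repeats that a response "must be confirmed by a second tumor assessment at least 8 weeks after the initial observed response". The Document History shows that the interval was chosen deliberately; the entry for Amendment 2.1 reads "Increase confirmation of primary endpoint from 4 weeks to 8 weeks after initial documentation". Section 9 says the SAP would be final before database lock.

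**SAP.** Section 6.3.1 says response "was confirmed by a second tumor assessment at least 4 weeks after the initial observed response". Section 9.2.10.1 defines a responder as a subject with a confirmed CR or PR and gives no interval, so 6.3.1 supplies it. Section 13.2 plans one ORR per cohort with an exact 95% CI, and a listing of all responses and tumor assessments. Section 9.1 says that efficacy endpoints will not be tested.

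**Timing and disclosure.** SAP 4 states "At the time of the database lock for RAIN-701 (23 April 2021), 41 subjects were enrolled", and says of the analysis methods that "they have been defined after the clinical database lock". The SAP is version 1.0, dated 14 October 2022. Section 15 quotes Protocol Section 7, records that "SAP Section 6.3.1 text instead states that the confirmation assessment must be at least 4 weeks after the initial observed response", and defends the new interval as one "which is aligned with the true RECIST v1.1 criteria". It does not mention Protocol 4.2.1.

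**The concern.** The confirmation interval is part of the primary endpoint's definition. It was changed after lock in an open-label trial (Protocol 4.1) where the local investigator assesses response (Protocol 9.6.1.2). Nothing in the documents says that responses were unknown to those who set the new rule. The loosening works in one direction, and the ORR that the protocol defined will not be tabulated beside the new one.

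The trial enrolled 11, 22 and 8 subjects in Cohorts A, B and C, so one reclassified subject visibly moves a cohort's estimate. SAP 4 also allows these analyses to be used in later manuscripts, which may not carry the subject listings.

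**Working it through.** **1. The plan's own figures.** The documents give no ORR under either rule. Their only figures for this endpoint are the design properties in Protocol 9.1 and SAP 7: stop if 3 or fewer of 21 respond, reject if 11 or more of 43 respond. With X1 ~ Bin(21, p) and X2 ~ Bin(22, p), the rejection probability is the sum over x = 4 to 21 of P(X1 = x) × P(X2 ≥ 11 − x).

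- p = 0.15: 0.04536 (stated 0.0454)
- p = 0.31: 0.80141 (stated 0.8014)
- Early stop at p = 0.15, P(X1 ≤ 3): 0.6113 (stated 0.61)

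All three reproduce. They are context only, because the test is not carried out.

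**2. Timing.** From 23 April 2021 to 14 October 2022 is 539 days, about 18 months.

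**3. Direction.** Let t be the days from first observed response to a confirming scan. If t ≥ 56 then t ≥ 28. Every subject confirmed under the 8-week rule is therefore confirmed under the 4-week rule, but not the reverse. With the denominator fixed, ORR under the 4-week rule is at least ORR under the 8-week rule.

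**4. Can routine scans be affected?** Scans are due every 56 days from Cycle 1 Day 1, each within ± 5 days (SAP 6.3.1).

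- Gap between consecutive scans: 56 − 10 = 46 to 56 + 10 = 66 days. Every gap passes 28 days; a gap of 46 to 55 days fails a strict 56.
- Assumption: whole-day offsets, uniform on −5 to +5 and independent. Of 11 × 11 = 121 pairs, 55 have the later scan's offset below the earlier one's, so 55/121 = 45% of gaps are under 56 days.
- Alternative assumption: the next scheduled scan, within its window, is accepted as the 8-week scan. Then 0% of routine gaps fail, and the rules differ only where an unscheduled scan is the sole confirmation.
- Two intervals span 112 − 10 = 102 to 112 + 10 = 122 days. A response that persists to a third scheduled scan is confirmed under both rules. Only responses not seen beyond the second scan can differ.

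**5. Size per subject.** Each subject confirmed only under the 4-week rule adds 1/n (enrolled n from SAP Table 1):

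| Cohort | n | Points added |
|---|---|---|
| A | 11 | 9.1 |
| B | 22 | 4.5 |
| C | 8 | 12.5 |
| All | 41 | 2.4 |

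For scale, with hypothetical counts in Cohort B: 3/22 = 13.6% (exact 95% CI 2.9 to 34.9) against 4/22 = 18.2% (5.2 to 40.3). The one-subject shift is small beside intervals 32.0 and 35.1 points wide.

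**6. The other change to ORR.** Protocol 9.6.1.2 divides by evaluable patients; SAP 9.2.11.1 divides by enrolled subjects. For a fixed number of responders the larger denominator gives a lower ORR, so this change can work the other way.

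**The case against.** The best defence is that the change is open, reasoned and of limited consequence. Section 15 names the protocol rule, states the replacement and gives a reason. The protocol itself presents 8 weeks as following RECIST v1.1, so the SAP was addressing an apparent inconsistency. The trial stopped at 41 subjects on a business decision, no efficacy test is planned, and Section 15 calls the efficacy analyses uninterpretable. Because every tumor assessment will be listed, a reader with the listings can rebuild the 8-week count. All of this stands.

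It does not fill the gap that remains. Disclosure explains why 4 weeks was chosen but does not show its effect. Section 15 also does not tell the reader that the primary endpoint definition in 4.2.1 is what changed. The two documents cite RECIST v1.1 for different intervals and cannot settle which is right; reporting both avoids having to.

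Several stronger readings are tempting but unsupported:

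- **The reported ORR must exceed the protocol's ORR.** The shorter interval may change nobody's status, and the denominator changed too, so the net shift has no fixed sign.
- **About 45% of responders would be lost under 8 weeks.** That figure describes scan gaps under assumed uniform, independent offsets and a strict 56-day count. Sites worked to an 8-week rule and could adjust scan dates (Protocol 7), so independence is doubtful.
- **Duration of response is altered as well.** SAP 9.2.12 starts it at first objective response and does not say confirmed, so the dependence is not established.
- **The rule was chosen to favour the drug.** The documents show when it was set, not why beyond the stated reason.

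**Conclusion.** The point holds as a reporting gap. A component of the primary endpoint was loosened after lock, and no ORR under the protocol's definition is planned beside the new one. For the confirmation rule alone, ORR can rise or stay the same and cannot fall; that conclusion needs no assumption beyond a common denominator.

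The size is not known. It is zero if no subject's status differs, and otherwise 9.1, 4.5 or 12.5 points per such subject in Cohorts A, B and C. Whether routine scans contribute depends on how the 8 weeks is counted, with 45% and 0% of consecutive gaps failing under the two sets of assumptions above.

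A reader might also infer an inflated type I error against the 15% null. The documents do not support that, because no test is done. The consequence is confined to descriptive estimates and any later publication of them.

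**What to change.** - In SAP 13.2, report confirmed ORR with exact 95% CI by cohort twice: under the protocol's 8-week rule and under the SAP's 4-week rule. Use the same denominator in both rows, so that any difference comes from the interval alone.
- State how the 8 weeks is counted: strictly 56 days, or with the ± 5-day scan window.
- In the response listing, flag subjects who meet only the 4-week rule.
- In SAP 15, cite Protocol 4.2.1 as the primary endpoint definition that changed, alongside Protocol 7.

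The cost is one extra table row per cohort and one listing flag, with no new data. The sponsor may have to show a less favourable figure beside the other; if no subject's status differs, the two rows will match and the question is closed.
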